**Sample Size:**

[figure not shown]
**Part 1:** The number of patients will depend upon the toxicities observed, the number of dose-level cohorts evaluated, and the number of dose-level cohorts expanded as the study progresses; approximately 30 patients are estimated. Overall sample size will be guided by the mCRM design.

**Part 2:** During the dose expansion phase of the study, up to 28 patients per each dose expansion cohort will be enrolled. Simon's two-stage design will be used. The null hypothesis that the true response rate is 7.5% will be tested against a one-sided alternative. In the first stage, 13 patients will be enrolled. If there are one (1) or fewer responses in these 13 patients, the

cohort will be closed. Otherwise, 15 additional patients will be enrolled for a total of 28 patients. The null hypothesis will be rejected if five (5) or more responses are observed in these 28 patients. This design yields a type I error rate of 0.05 (one-sided) and power of 80% when the true response rate is 25%.

In the basket group, up to 24 patients will be enrolled, with no more than 3 patients from each indication. If responses are observed, plans are described in the Interim Analysis [Part 2]).

Figure 1: ADCT-502-101 Study Schematic

## Schedule of Events

**Table 1: Schedule of Events**

	Screening	Cycle 1					Cycle 2					Cycles 3, 4, 5, etc.		EOT	12-Week Follow-up 	Long-term Follow-up
	Days -28 to -1	Day 1	Day 2	Days 3 and 5	Day 8	Day 15	Day 1	Day 2	Days 3 and 5	Day 8	Day 15	Day 1	Day 8 			
Informed consent 	X															
Demography 	X															
Medical/Cancer history 	X															
Available tumor tissue collection 	X															
Physical examination 	X	X 			X	X	X 			X	X	X 		X		
ECOG PS 	X	X					X					X		X		
Height	X															
Weight	X	X					X					X		X		
Vital signs 	X	X	X	X	X	X	X	X	X	X	X	X	X			
12-lead ECG (triplicate) 	X	X	X				X	X				X		X		
ECHO or MUGA 	X						X					X		X		
Disease assessments 	X											X 		X 		X 
β-HCG 	X	X										X 		X		
CBC with differential 	X	X			X	X	X			X	X	X	X			

	Screening	Cycle 1					Cycle 2					Cycles 3, 4, 5, etc.		EOT	12-Week Follow-up 	Long-term Follow-up
	Days -28 to -1	Day 1	Day 2	Days 3 and 5	Day 8	Day 15	Day 1	Day 2	Days 3 and 5	Day 8	Day 15	Day 1	Day 8 			
Coagulation 	X	X					X					X		X		
Chemistry 	X	X			X	X	X			X	X	X	X	X		
Urinalysis 	X	X					X					X		X		
PK sample 		X	X	X	X	X	X	X	X	X	X	X		X	X	
ADA sample 	X	X					X					X		X	X	
sHER2 sample 		X					X					X		X	X	
[REDACTED]			[REDACTED]											[REDACTED]		
Concomitant medications 	<	X										→				
Adverse events 	<	X										→				
ADCT-502 administration 		X					X					X				
1 st New anticancer treatment 														X	X	
Survival																X 

**Visit Scheduling Windows:** For scheduling purposes, the following allowances will be made for Visits:

- Day 1: Cycles 2, 3, 4, etc. (excluding Cycle 1, Day 1): ± 3 days
- Days 8 and 15: ± 1 day
- EOT: As soon as possible after decision to discontinue the study drug AND prior to initiation of new anticancer treatment
- 12-Week Follow-up: ± 7 days after last dose of study drug
- Long Term Follow-Up (approx. every 12 weeks after last dose): ± 4 weeks

Refer to **Section 10.2** for details of CBC, coagulation, chemistry, and urinalysis panels.

-  If possible, collection of pharmacokinetic (PK), soluble HER2, and anti-drug antibodies (ADA) samples will take place at the follow-up visit 12 weeks after the last dose of ADCT-502, unless a new anticancer treatment has been initiated.
-  After completion of 6 treatment cycles, the Day 8 visit is not required unless clinically indicated.
-  A signed and dated Institutional Review Board (IRB) /Independent Ethics Committee (IEC) approved informed consent form (ICF) obtained prior to performing any study evaluations. Results (e.g., from laboratory tests or radiographic evaluations, etc.) obtained prior to the date of informed consent, but within the allowed timeframe for Screening may be used for determination of patient eligibility only if obtained as part of the patient's standard of care. Patients must meet entry criteria at Screening, and should continue to meet entry criteria at Cycle 1 Day 1 pre-dose. However, clinically acceptable variations, if they are in the opinion of the Investigator not compromising patient safety, may be allowed on that day.
-  Demography includes collection of date of birth, sex, and race.
-  Medical/Cancer history to include a complete history of all surgeries, significant diagnoses, and all cancer treatments. Results of testing for genetic abnormalities associated with the patient's tumor type (such as BRCA1, for example) will be recorded.
-  During Part 1, ship tissue sample to the central laboratory for **retrospective analysis of HER2**. An FFPE block (or slides) from any biopsy since initial diagnosis is acceptable, but if several are available, the most recent sample is preferred. Either tumor tissue block or freshly cut unstained slides (minimum 7; 10 preferred) is acceptable. During Part 2, ship tissue sample to the central laboratory for **prospective analysis of HER2** to confirm eligibility.
-  Physical examinations will include a complete review of body systems. Investigators should be cognizant of potential toxicities for ADCT-502 and similar compounds as described in the Investigator's Brochure (IB) and refer unexplained findings or abnormalities to a specialist accordingly (e.g., ocular toxicity to an ophthalmologist, etc.).
-  A physical examination does not need to be repeated if performed within 72 hours prior to Day 1 of any cycle.
-  Refer to [Appendix 18.2](#) for definitions of Eastern Cooperative Oncology Group (ECOG) Performance Status grades.
-  Refer to [Table 2](#) for timing of vital sign measurements. Vital sign measurements include arterial blood pressure, heart rate, respiratory rate, and body temperature.
-  The Fridericia formula for rate correction of QT intervals should be used for all patients throughout the study. Refer to [Table 2](#) for timing of electrocardiogram (ECG) in relation to PK sample collection.
-  Perform multiple-gated acquisition (MUGA) scan or echocardiogram (ECHO) at Screening, after Cycle 1, every 3 cycles (i.e., every 9 weeks), and at End of Treatment (EOT). All patients will have measurements of left ventricular ejection fraction (LVEF) via a consistent method (MUGA scan or ECHO), regardless of symptoms. If the LVEF is reported as a range, the average should be taken.
-  Screening (Baseline) imaging (computerized tomography [CT] or magnetic resonance imaging [MRI]) must be performed within 4 weeks prior to Day 1, Cycle 1. See [Section 10.3](#) for details.
-  Disease assessments will be conducted every 2 cycles  $\pm$  1 week for the first 2 time points (e.g., after Cycles 2 and 4), and every 4 cycles thereafter (i.e., approximately every 12 weeks). Patients with metastatic breast cancer (MBC) enrolled in Groups A and B will have disease assessments every 4 cycles.

.....Footnotes continue on next page

-  Disease assessments do not need to be repeated at EOT if last assessment was performed within 6 weeks prior to the EOT visit, or if patient already has documented progression of disease (PD).
-  Any patients who discontinue treatment for any reason other than disease progression will continue to be followed by radiographic examination every 12 weeks until disease progression or initiation of new anticancer treatment. Once the final efficacy analysis for progression-free survival (PFS) is performed (Part 2), the frequency of tumor response assessment for patients remaining under treatment may be further decreased and/or performed according to standard of care.
-  Blood or urine pregnancy test for women of childbearing potential. For eligibility confirmation, a negative blood pregnancy test is required; the test does not need to be repeated if it was obtained within 7 days prior to Cycle 1, Day 1.

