#### 4.6.2 Definition of Dose-Limiting Toxicities

A DLT is defined as any of the following events that occur during the 21-day DLT evaluation period, except those that are clearly due to underlying disease or extraneous causes.

A hematologic DLT is defined as:

Event	Severity
Febrile neutropenia or neutropenic infection	Grade 3 or 4
Neutropenia lasting > 7 days	Grade 4
Thrombocytopenia	Grade 4
Thrombocytopenia with clinically significant bleeding	Grade 3
Thrombocytopenia requiring a platelet transfusion	Grade 3
Anemia	Grade 4
Anemia requiring transfusion	Grade 3

A non-hematologic DLT is defined as:

Event	Severity
Hy's law case	AST and/or ALT > 3x ULN and bilirubin > 2x ULN, and without initial findings of cholestasis (serum alkaline phosphatase (ALP) activity < 2x ULN) and no other reason that could explain the combination of increased transaminases and serum total bilirubin, such as viral hepatitis A, B, or C, preexisting or acute liver disease, or another drug capable of causing the observed injury.
Hypersensitivity/infusion-related	Grade 3 or higher. A Grade 3 hypersensitivity /

reaction (regardless of premedication)	infusion-related reaction that resolves within 24 hours after onset with appropriate clinical management does not qualify as a DLT.
All other non-hematologic toxicity	Grade 3 & 4

The following conditions are not considered non-hematologic DLTs:

Event	Severity
Fatigue	Grade 3 for $\leq$ 7 days.
Diarrhea, nausea, or vomiting	Grade 3 in the absence of premedication that responds to therapy and improves by at least 1 grade within 3 days for Grade 3 events or to $\leq$ Grade 1 within 7 days.
Serum lipase or serum amylase	Grade 3 for $\leq$ 7 days if without clinical signs or symptoms of pancreatitis.
Electrolyte abnormalities	$\leq$ Grade 3 which normalize within 48 hrs (with or without medical intervention) and which do not manifest themselves clinically; in such instance, a follow-up sample MUST be taken within 48 hrs to check whether such normalization has occurred.

Patients who experience a DLT that resolves or stabilizes with appropriate medical management may continue treatment at the discretion of the Investigator in consultation with the Sponsor.

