### **12.4.2 Clinical Laboratory Results**

Clinical hematology, coagulation panel, biochemistry, and urinalysis data will be summarized at each scheduled assessment. All results will be summarized using shift from baseline. Shifts for clinical laboratory results that can be graded according to CTCAE version 4.0 will be summarized by CTCAE grade. Shifts for other numeric laboratory results will be by high/normal/low flag. Shifts for all other laboratory results will be by normal/abnormal flag.

Summaries by visit will include data from scheduled assessments, and all data will be reported according to the nominal visit date for which it was recorded. Unscheduled data will be included in “worst-case post-Baseline” summaries, which will capture a worst case across all scheduled and unscheduled visits after the first dose of study treatment. Further details will be provided in the SAP.

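### Table 1 schedules no CBC at the End of Treatment visit, so new or asymptomatic late cytopenia after the last scheduled count has no mandated measurement

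*Protocol*

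**What the plan says.** Protocol Table 1 marks the row "CBC with differential 19" at Screening, on Days 1, 8 and 15 of Cycles 1 and 2, and on Days 1 and 8 of later cycles. The EOT cell is empty. Footnote 2 thins the later schedule: "After completion of 6 treatment cycles, the Day 8 visit is not required unless clinically indicated".

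The other three laboratory rows are chemistry, "Coagulation 19" and "Urinalysis 19". All three are marked at EOT, and so are "12-lead ECG (triplicate) 11" and the ECHO or MUGA row. Footnote 19, shared by the four laboratory rows, only waives a repeat when a test was done in the 72 hours before a Day 1.

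On analysis, Section 3.2.1 puts laboratory abnormalities in the primary endpoint, and Section 12.4.2 states: "Clinical hematology, coagulation panel, biochemistry, and urinalysis data will be summarized at each scheduled assessment". Section 12.4.1 and SAP Section 4.8.2.1 run the TEAE window to 30 days after the last dose. SAP Section 4.8.3 keeps the shift-from-baseline laboratory tables.

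**The concern.** The blank looks like an oversight rather than a choice. Blood is drawn at EOT for chemistry and coagulation, yet the panel that would show a low platelet, neutrophil or hemoglobin value is not among the tests. Section 5.2 is given over to hematologic toxicity, and several of its rules end in permanent discontinuation, so some patients will reach EOT because of a cytopenia.

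At stake is uniform ascertainment of a primary-endpoint safety measure. As written, Section 12.4.2 has an EOT time point to summarize for chemistry, coagulation and urinalysis, but none for hematology. A cytopenia that appears after the last scheduled count and causes no symptoms is recorded only if someone chooses to test.

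**Working it through.** **Step 1. Read the rows.** Table 1 has 16 visit columns. Each row below has 16 cells, so a shifted column is unlikely.

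| Row | Marked visits other than EOT | EOT |
|---|---|---|
| CBC | Screening; Days 1, 8, 15 of Cycles 1 and 2; Days 1, 8 of Cycles 3+ | blank |
| Chemistry | the same nine visits | X |
| Coagulation | Screening; Day 1 of every cycle | X |
| Urinalysis | Screening; Day 1 of every cycle | X |
| Triplicate ECG | Screening; Days 1, 2 of Cycles 1 and 2; Day 1 of Cycles 3+ | X |
| ECHO/MUGA | Screening; Day 1 of Cycle 2 and of Cycles 3+ | X |
| Physical examination | Screening; Days 1, 8, 15 of Cycles 1 and 2; Day 1 of Cycles 3+ | X |
| Vital signs | Screening and every treatment visit | blank |

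CBC and chemistry agree at 1 + 3 + 3 + 2 = 9 visits and differ only at EOT.

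**Step 2. Look for a CBC elsewhere.** Section 7.1 asks for all assessments due at EOT but does not list them. Section 10 refers back to Tables 1 and 2. Table 2 is blacked out, but by its title it covers ECG, vital signs and exploratory samples. No section adds a CBC at EOT or says why it is left out.

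**Step 3. Size the gap.** Inputs: the CBC days from Table 1, footnote 2, and the 30-day TEAE window. Count the last dose (Day 1) as day 0, take the Day 1 CBC as pre-dose (an assumption, consistent with footnote 19), and assume that the patient does not attend the next Day 1.

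Days with no scheduled CBC = 30 − (days from last dose to last scheduled CBC)

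| Last dose in | Last scheduled CBC after it | Days left uncovered |
|---|---|---|
| Cycles 1-2 | Day 15 = +14 | 30 − 14 = 16 |
| Cycles 3-6 | Day 8 = +7 | 30 − 7 = 23 |
| Cycle 7 or later | none (Day 8 only if clinically indicated) | 30 − 0 = 30 |

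The ±1 day window on Days 8 and 15 moves the first two results to 15-17 and 22-24 days. If the patient does attend the next Day 1 of the 21-day cycle, a CBC is scheduled at +21 and 30 − 21 = 9 days remain, or 6-12 with that visit's ±3 day window.

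**Step 4. Effect of the change.** With an X at EOT, the CBC row becomes identical to the chemistry row. The protocol times EOT only as soon as possible after the decision to stop, so the number of days recovered cannot be computed.

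**The case against.** The case for leaving the schedule alone has real force.

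- *Counts after the last dose exist.* Through Cycle 6 at least one scheduled CBC follows each dose. A reader might infer that hematologic toxicity goes entirely unobserved after the last dose; Table 1 does not support that.
- *Known cytopenias are followed.* Sections 7.1 and 11.6 require events that lead to discontinuation to be followed until resolved, stable, chronic or not clinically significant, and Section 11.3 records resolution date and outcome. It would be wrong to infer that recovery is never captured. This stands, and it confines the gap to new or asymptomatic late cytopenia.
- *Unscheduled values count.* Section 12.4.2 and SAP Section 6.1.2 use them for worst values and grades. A reader might conclude that the worst hematologic grade is biased downward, but the documents hold no data to show it. What remains is that unscheduled testing is discretionary and so not uniform across patients.
- *DLT assessment is largely untouched.* DLTs count only in the first 21 days, which have CBCs on Days 8 and 15, with Cycle 2 Day 1 following. The exception is a patient who stops during Cycle 1 and has no Cycle 2 Day 1 visit. Seven listed DLT rows are hematologic (for example "Thrombocytopenia requiring a platelet transfusion") against three non-hematologic, but one of those three covers all other Grade 3 and 4 toxicity and no frequencies are given. The row count does not make hematologic events the largest DLT category.
- *An EOT count is an imperfect remedy.* If EOT falls soon after a dose, it may miss a late nadir. If the decision to stop is taken at a planned Day 1, a CBC is due that day anyway. Both points stand.
- *The mark may have been lost.* Sixteen cells per row rule out a shifted column, not a dropped X.

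**Conclusion.** The point holds in a limited form. As extracted, Table 1 omits CBC at EOT while scheduling the other three laboratory panels there, and nothing in the protocol or SAP supplies or justifies the omission. The uncovered part of the 30-day TEAE window is about 16, 23 or 30 days according to the cycle of the last dose. These figures assume no attendance at the next Day 1, a pre-dose Day 1 CBC and no clinically indicated Day 8 visit from Cycle 7. The documents do not say how many patients stop in each of these periods, so no number of missed events can be given.

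The finding concerns uniform measurement of late cytopenia. It is not evidence that events were missed or that the DLT-based dose decisions were wrong. It is worth correcting because the change is small and serves a primary-endpoint safety measure.

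**What to change.** Check the source PDF page first. If the cell is blank there:

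1. Put an X for CBC with differential in the EOT column of Table 1, drawn with the chemistry and coagulation samples, or state why it is omitted.
2. Check the vital signs row at EOT in the same pass, since vital signs are also in the primary endpoint (Section 3.2.1).
3. Leave the analysis rules as they are. The worst-case rule in Section 12.4.2 would take in the new value automatically.

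The cost is one table cell and one extra tube per patient, analysed locally, at a blood draw that already takes place. The gap becomes narrower but does not close, because EOT is not tied to a fixed day after the last dose.

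SAP Section 3.3 records that the trial ended early with only Part 1 performed. For this study, the practical step is therefore a sentence beside the hematology shift tables saying that no CBC was scheduled at EOT. The table correction matters for any further amendment or reuse of the schedule.

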## List of Abbreviations

Abbreviation	Definition
ADA	anti-drug antibodies
ADC	antibody drug conjugate
ADL	activities of daily living
anti-HCV	antibody to hepatitis C virus
ASCO	American Society of Clinical Oncology
AUC	area under the concentration versus time curve
$\beta$ -HCG	beta human chorionic gonadotropin
BID	twice a day (bis in die)
BSA	body surface area
CAT or CT	computerized tomography
CBC	complete blood count
cfDNA	circulating free DNA
CLIA	Clinical Laboratory Improvement Amendments
$C_{\max}$	maximum serum concentration
CNS	central nervous system
CR	complete response
CRC	colorectal cancer
CSF	cerebrospinal fluid
DAR	drug to-antibody ratio
DCR	disease control rate
DESC	dose escalation steering committee
DLT	dose limiting toxicities
DOR	duration of response
DSMB	data safety monitoring board
ECHO	echocardiogram
ECOG	Eastern Cooperative Oncology Group
ECOG PS	Eastern Cooperative Oncology Group Performance Status
eCRF	electronic case report form
EGFR	epidermal growth factor receptor
EOI	end of infusion
EOT	end of treatment
EWOC	escalation with overdose control
FDA	Food and Drug Administration
FIH	first-in-human
FISH	fluorescence in situ hybridization
FFPE	formalin-fixed paraffin-embedded
HBsAg	hepatitis B surface antigen
HER2/neu receptor	human epidermal growth factor receptor-2
HED	human equivalent dose
HIV	human immunodeficiency virus
HNSTD	highest non-severely toxic dose
HR	hazard ratio

[REDACTED]	[REDACTED]
G/GE	gastric/gastroesophageal
GLP	good laboratory practices
IB	Investigator's Brochure
IHC	immunohistochemistry
ISH	in situ hybridization
IV	intravenous
LHRH	luteinizing hormone-releasing hormone
LVEF	left ventricular ejection fraction
mAb	monoclonal antibody
MBC	metastatic breast cancer
mCRM	modified continual reassessment method
MedDRA	Medical Dictionary for Regulatory Activities
MI	myocardial infarction
mPFS	median progression-free survival
MRI	magnetic resonance imaging
MTD	maximum tolerated dose
MUGA	multigated acquisition
mOS	median overall survival
NCI CTCAE	National Cancer Institute Common Terminology Criteria for Adverse Events
NGS	next generation sequencing
NSCLC	non-small cell lung cancer
ORR	overall response rate
OS	overall survival
PBD	pyrrolobenzodiazepine
PD	pharmacodynamics
PDX	patient derived xenograft
PFS	progression-free survival
PK	pharmacokinetic
PO	per os
PS	performance status
RDE	recommended dose for expansion
RECIST	Response Evaluation Criteria in Solid Tumors
SAE	serious adverse event
SCLC	small cell lung cancer
sHER2	soluble HER2
SUSARs	Suspected Unexpected Serious Adverse Reactions
TEAE	treatment-emergent adverse event
T max	time to C max
U	United States

## 1 Introduction and Background

### 1.1 HER2 and HER2 Targeting Therapies

The human epidermal growth factor receptor-2 (HER2/neu receptor), a member of the epidermal growth factor family of receptor tyrosine kinases (including EGFR/ErbB1/HER1, ErbB3/HER3, and HerbB4/HER4), is a 185 kDa transmembrane glycoprotein, which provides signal transduction for cell proliferation and differentiation. The HER2 monomeric protein has three main regions: the extracellular amino-terminal region comprising four subdomains (I-IV), the hydrophobic transmembrane domain and the carboxy-terminal kinase domain comprising the juxtamembrane domain, tyrosine kinase and C-terminal tail with autophosphorylation sites. HER2 has no known ligand, and it is activated by homodimerization or heterodimerization with other member of the ERBB family ([Omar, 2015](#)).

HER2 is over-expressed/amplified in several solid tumor types ([Yan, 2015](#)). Targeted HER2 therapies are approved for the treatment of breast and gastric/esophageal cancers that over-express or are gene-amplified for HER2.

Trastuzumab (Herceptin®), a humanized monoclonal antibody (mAb), binds to the HER2 receptor and downregulates its expression on the cell surface. Trastuzumab is approved in the United States (US) and in Europe for the treatment of HER2-positive breast cancer in the adjuvant and metastatic settings, defined as HER2 IHC (immunohistochemistry) 3+ or IHC 2+/ fluorescence in-situ hybridization (FISH)-amplification ([Herceptin® \[trastuzumab\] US Prescribing Information, 2016](#)). In the metastatic setting, trastuzumab is used in combination with chemotherapy regimens and/or in combination with pertuzumab in the first-line setting (CLEOPATRA study) ([Swain, 2015](#)) followed by ado-trastuzumab emtansine (T-DM1) after relapse or disease progression. Despite improved patient outcomes, acquired resistance affects the majority of patients previously exposed to trastuzumab, and the molecular mechanisms conferring trastuzumab resistance are likely to be multifactorial.

In addition, trastuzumab is indicated in combination with cisplatin and capecitabine or 5-fluorouracil for the treatment of patients with HER2 overexpressing metastatic gastric or gastroesophageal junction adenocarcinoma, who have not received prior treatment for metastatic disease (ToGA trial) ([Bang, 2010](#)). Trastuzumab-based therapy significantly improved median overall survival (mOS) compared with the chemotherapy alone (hazard ratio [HR] 0.74; p=0.0046 and mOS: 13.8 months versus 11.1 months). However, acquired resistance to trastuzumab usually limits the duration of response to this treatment despite its improvement over the chemotherapy alone (duration of response [DOR]) 6.9 months versus 4.8 months).

Ado-trastuzumab emtansine (Kadcyla®), also known as T-DM1, is an antibody-drug conjugate of trastuzumab containing a potent microtubule inhibitor, DM1 (a derivative of maytansine) approved in the US in 2013 for the treatment of HER2-positive metastatic breast cancer for patients who had previously been treated with trastuzumab and a taxane chemotherapy (EMILIA study) ([Verma, 2012](#)). Median progression-free survival (mPFS) was 9.6 months with T-DM1 versus 6.4 months with lapatinib plus capecitabine (HR for

progression or death from any cause, 0.65;  $P<0.001$ ), and mOS at the second interim analysis crossed the stopping boundary for efficacy (30.9 months versus 25.1 months; HR for death from any cause, 0.68;  $P<0.001$ ). Ado-trastuzumab emtansine (T-DM1) has also demonstrated the potential to prolong PFS in the third-line setting based on results from the Phase 3 TH3RESA study ([Krop, 2014](#)) (mPFS 6.2 months for T-DM1 versus 3.3 months for physician's choice). However, results from the Phase 3 MARIANNE study ([Perez, 2016](#)) indicate that median PFS in the frontline setting for patients with advanced breast cancer treated with T-DM1 was non-inferior, but not superior, compared to those treated with trastuzumab plus a taxane-based chemotherapy. Ado-trastuzumab emtansine is often accompanied by unacceptable thrombocytopenia and hepatotoxicity at doses higher than the approved regimen (3.6 mg/kg every 3 weeks), as well as reductions in left ventricular ejection fraction (LVEF), and peripheral sensory neuropathy. In preclinical gastric cancer models, T-DM1 has shown more potent antitumor activity than trastuzumab ([Barok, 2011](#)). However, the multicenter adaptive phase 2/3 of T-DM1 in HER2-positive patients with unresectable locally advanced or metastatic gastric or gastroesophageal (GE) junction cancer who progressed during or after first-line fluoropyrimidine plus platinum therapy with or without HER2-targeted therapy did not show a benefit of T-DM1 vs. taxane based chemotherapy ([Kang, 2016](#)).

The third HER2 targeting mAb based therapeutic modality currently approved in the oncology setting, is pertuzumab (PERJETA®). Pertuzumab is a HER2/neu receptor antagonist indicated for use in combination with trastuzumab and docetaxel for treatment of patients with HER2-positive metastatic breast cancer (MBC) who have not received prior anti-HER2 therapy or chemotherapy for metastatic disease. It is also approved in combination with trastuzumab and docetaxel as neoadjuvant treatment of patients with HER2-positive, locally advanced, inflammatory, or early stage breast cancer as part of a complete treatment regimen for early breast cancer ([PERJETA ® US Prescribing Information, 2012](#)).

In the Phase 3 randomized trial (CLEOPATRA study) ([Swain, 2015](#)) of pertuzumab plus trastuzumab and docetaxel vs. placebo plus trastuzumab and docetaxel, independent review indicated that the pertuzumab-treated group demonstrated an increase in mPFS of 6.3 months (18.7 months in the pertuzumab -treated group vs. 12.4 months in the placebo-treated group).

Approximately 20% of all cases of breast cancer have *HER2* gene amplification and high levels of *HER2* protein expression that predict the response to trastuzumab. Gastric cancer is the fourth most commonly diagnosed cancer and the second most common cause of cancer-related deaths worldwide. *HER2* over-expression/amplification occurs in 7–34% of gastric cancer and is associated with poor prognosis. While trastuzumab based therapy is the standard of care in both metastatic breast and gastroesophageal cancer, the known prevalence of *HER2* over-expression/amplification across tumor types in general suggests that other patient populations may benefit from treatment with *HER2* targeted agents. A number of smaller studies or case reports have demonstrated this, for example in patients with colorectal cancer (CRC) ([Sartore-Bianchi, 2016](#); [Harder, 2012](#); [Javle, 2015](#); [de Bono, 2007](#); [Bookman, 2003](#); [Fleming, 2010](#); [Oudard, 2015](#); [Limaye, 2013](#)).

In one of the largest studies to date, (Yan, 2015) HER2 expression status in diverse cancers was examined in approximately 38,000 patients. Indications planned for inclusion in this protocol were found to be positive in the range of 0.6% (prostate) to 12.4% (bladder carcinoma). Since these percentages of HER2 positive patients refer to what is termed HER2-high in this protocol, the percentage of patients anticipated to ultimately benefit from ADCT-502 may be higher, as patients with HER2-low expressing tumors were not evaluated but will be included in this protocol in a staggered fashion, depending on efficacy results in HER2-high expressing patients.

In certain malignancies, principally non-small cell lung cancer (NSCLC), the HER2 protein can be constitutively activated through genetic mutations; initial efficacy data suggest that HER2 targeting modalities can also be of therapeutic benefit for such patients (Mazieres, 2013).

